Study Title: Quantifying the Trainability of Peripheral Nerve Function in Young and Older Adults.

Study Registration Number: IRB-22-270

Principal Investigator [name]
Professor and Chair of Exercise Science
Neural Health Research Laboratory
Syracuse University, Syracuse, NY, United States
(Previously at Oklahoma State University)

NCT number N/A

Version 2.0

Date 9/17/2024

Author [name]
Postdoctoral Research Assistant
Neural Health Research Laboratory
Syracuse University, Syracuse, NY, United States
(Previously at Oklahoma State University)

SIGNATURE PAGE

AUTHOR: Name: [name]
Professor and Chair

Name: [name]
Postdoctoral Research Assistant

Abbreviations

SAP	Statistical Analysis Plan
NCV	Nerve Conduction Velocity
nCSA	Nerve Cross-Sectional Area
FDS	Flexor Digitorum Superficialis
ANOVA	Analysis of Variance

1. Introduction

The primary objective of this study was to quantify the effects of hand grip resistance training on nerve function in young and older adults (primary aim) and to determine if training affects nerve cross-sectional area, maximal hand grip strength, and hand motor dexterity (secondary aims).

The statistical analysis plan (SAP) provides details of the statistical methods used during the analyses of data collected within the scope of IRB-22-270 and was prepared in accordance to IRB-22-270 (version 1; 9-9-2024).

2. Overview & Objectives of Study Design

This study consisted of four arms, first separated by age based on our target ranges (young = 18-35 yrs old, and older = 60+ yrs old), and then pseudo-randomly assigned to either the intervention group or control group. Conditions of inclusion were apparently healthy adults between the ages of 18 – 100 years old. Individuals with any of the following exclusion criteria were not permitted to participate: 1.) If you have been notified by a physician to refrain from exercise due to cardiovascular issues, 2.) Known orthopedic or neuromuscular limitations or illness of the upper extremities, 3.) Known neuromuscular disorders, and 4.) Individuals that were experiencing a fever ($> 100.4^{\circ}$ F) or had identified as symptomatic on the COVID-19 screening questionnaire were not permitted to participate.

Participants assigned to the intervention group performed bilateral hand grip resistance training 3×/week for 4 weeks using a specialized hand-grip kit provided to them. This included Arm 1 (Young Training Group) and Arm 3 (Older Training Group). Participants were provided with pictures and instructions for each exercise upon completion of visit 1. Those assigned to the control group were asked to maintain normal daily activities throughout the duration of the four weeks. This included Arm 2 (Young Control Group) and Arm 4 (Older Control Group).

Laboratory testing visits were performed at two time points: visit 1 (before the intervention) and visit 2 (after four weeks) at which nerve conduction velocity, nerve cross-sectional area, maximal hand grip strength, and hand motor dexterity were measured.

3. Sample Size Justification

Power calculations indicated that a sample size of > 16 was sufficient power (Cohen's $d = > -0.80$) with the alpha set at 0.05 (G*Power v. 3.1, Dusseldorf, Germany). Therefore, recruitment of 80 participants pseudo-randomly assigned to 1 of 4 groups (control vs training: young; control vs training: old) should ensure a large enough sample size (>16) to report alterations in nerve conduction velocity as a result of resistance training.

4. Aims and Objectives

To quantify the effects of resistance training on nerve conduction velocity in young and older adults and to determine if age affects nerve plasticity in response to training.

5. Outcomes

This section will present the outcomes investigated to answer the study aims and objectives. Analyses are described in section 6 analysis.

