5.3 Safety Outcomes

Adverse events

If adverse events occurred, adverse events were reported at each visit.

6. Analyses

All statistical analyses were performed using SPSS Version 26 (IBM, Armonk, NY, USA). Two four-way mixed factorial ANOVA model's (age [young vs old] \times group [training vs. control] \times time [pre vs. post] \times limb [left vs. right]) were conducted to determine changes in NCV, nCSA, max strength, and dexterity. If warranted, dependent paired samples t-test were run. An alpha level of 0.05 was used for all comparisons.

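### Does an inclusion range of 18–100 years leave people aged 36–59 eligible for the trial but without an arm or a level of the age factor?

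*Combined protocol and SAP*

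**What the plan says.** Section 2 describes four arms, "first separated by age based on our target ranges (young = 18-35 yrs old, and older = 60+ yrs old", with pseudo-random assignment to training or control coming after that separation. The next sentence gives the age criterion: "Conditions of inclusion were apparently healthy adults between the ages of 18 – 100 years old". Four exclusion criteria follow: medical advice against exercise, upper-limb limitation, neuromuscular disorder, and fever or COVID-19 symptoms. None concerns age.

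The arms are then named. For training: "This included Arm 1 (Young Training Group) and Arm 3 (Older Training Group". For control: "This included Arm 2 (Young Control Group) and Arm 4 (Older Control Group". Section 3 plans "recruitment of 80 participants pseudo-randomly assigned to 1 of 4 groups (control vs training: young; control vs training: old". The ANOVA in Section 6 carries the factor "age [young vs old", with two levels. No section says what was done with a volunteer aged 36 to 59.

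**The concern.** Two adjacent sentences in Section 2 give different age limits. A healthy person of 45 meets the inclusion sentence and none of the exclusions, yet is neither young nor older as the arms define those terms. The ranges are called targets, which could be read as a recruitment aim and not a limit.

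This matters because one aim in Section 4 is whether age alters the nerve's response to training, and the make-up of the two age groups defines that comparison. If mid-age people were placed in the nearest arm, the young–old contrast would be blurred. If they were enrolled and later removed, the sample would fall below the planned 80 by a decision the plan does not describe.

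**Working it through.** **The plan's own figure.** The only computed figure is the sample size of more than 16 in Section 3, at a Cohen's d of 0.80 in size and alpha 0.05. Test, sidedness and target power are not stated, so it cannot be strictly reproduced. Assuming a two-sided paired t-test, n = 15 is the smallest size reaching 80% power, n = 16 gives 84.8% and n = 17 gives 87.2%, so the figure is compatible with a pre/post comparison within one group. The age question does not depend on it, except as the plan's yardstick for losses below.

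**Size of the gap in the wording** (whole years, Section 2):
- Inclusion range: 100 − 18 + 1 = 83 ages.
- Young range: 35 − 18 + 1 = 18 ages. Older range up to 100: 100 − 60 + 1 = 41 ages.
- Ages with no arm: 83 − 18 − 41 = 24 (36 to 59), and 24/83 = 28.9%.

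This counts calendar ages. It says nothing about how many participants, if any, were in the gap.

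**What happens if the text is followed.** The order in Section 2 is separation by age range, then assignment within age group. A person of 45 fails the first step and never reaches the second. All four arms in Section 2, the four groups in Section 3 and both levels of the factor in Section 6 are young or older. The title and the objective in Section 1 also speak only of young and older adults. The inclusion sentence is the one place where the wider span appears, and it works as an outer limit within which the two ranges select.

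**If people were lost.** Assume an equal split, 80/4 = 20 per arm, and assume 4 people aged 36–59 were dropped: (80 − 4)/4 = 19, which is above 16. More generally, 17 per arm needs 4 × 17 = 68, so up to 80 − 68 = 12 losses spread evenly would still meet the plan's criterion, taken as a per-arm figure.

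**If people were misplaced.** Let a share m of one age group, equal in its training and control arms, be mid-age with a training response halfway between young and old (both assumed). That group's training effect moves by m × 0.5 of the young–old difference D, so the contrast becomes D × (1 − m/2):
- m = 10%: 0.95 D, a 5% shrinkage.
- m = 20%: 0.90 D, a 10% shrinkage.

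The document supplies no value for m. Any m above zero requires that the stated arm definitions were broken.

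**The case for a change.** The strongest case for a change is that the sentence labelled as inclusion is the eligibility rule, while a target range is only an intention. A reader cannot tell from the document whether people aged 36–59 were never enrolled, were put in the nearest arm, or were removed later. The last two would be decisions made after enrolment that bear on a stated aim, and one sentence would settle the matter.

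Part of this stands. The inclusion sentence is loose, and the handling of ages 36–59 is nowhere stated. It does not follow that a mid-age person must be misplaced or dropped after enrolment. That pair of outcomes leaves out the natural one, which is non-enrolment because the person falls in neither range.

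Nor would rewriting eligibility be harmless. Section 2 reports the criteria in the past tense, and Section 1 says the SAP was prepared in line with an IRB version that is not available here to check. Replacing 18–100 with two narrower ranges could misstate the criterion in force when people were recruited.

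**Conclusion.** No change to the plan follows. The mismatch in Section 2 is real but is one of wording: 24 of 83 nominally eligible ages have no arm. Followed as written, the age separation keeps those ages out of every arm and every model cell, so the arms, the age factor and the age-by-training comparison stay sound.

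No effect on the estimate or on the sample size is shown. The dilution of 5–10% rests on assumed shares of 10–20% and on breaches of the arm definitions. The assumed loss of 4 people leaves an average of 19 per arm against a criterion of more than 16.

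The conclusion rests on reading the two ranges as the condition for entering an arm, and on the absence of any report that someone aged 36–59 took part. If such people had been enrolled, an analyst using a young/old factor with stated limits would leave them out of it and give their number in the participant flow. That is ordinary reporting and needs no new rule.

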5.1 Primary Outcome

Nerve conduction velocity (NCV) of the Flexor Digitorum Superficialis (FDS) muscle. It was measured at visit 1 and visit 2 (four weeks apart).

5.2 Secondary Outcomes

- Nerve cross-sectional area (nCSA).
- Maximal hand grip strength (kg)
- Hand motor dexterity (time, in seconds, to task completion)

Other laboratory parameters

n/a

5.3 Safety Outcomes

Adverse events

If adverse events occurred, adverse events were reported at each visit.

6. Analyses

All statistical analyses were performed using SPSS Version 26 (IBM, Armonk, NY, USA). Two four-way mixed factorial ANOVA model's (age [young vs old] \times group [training vs. control] \times time [pre vs. post] \times limb [left vs. right]) were conducted to determine changes in NCV, nCSA, max strength, and dexterity. If warranted, dependent paired samples t-test were run. An alpha level of 0.05 was used for all comparisons.

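### Section 6 has no missing-data rule, and its ANOVA in standard form drops anyone lacking one of four values; a mixed model would keep them, for a conditional and modest gain

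*Combined protocol and SAP*

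**What the plan says.** Section 6 names SPSS 26, "Two four-way mixed factorial ANOVA" models with age and group between participants and time and limb within participants, and a two-part follow-up condition: "If warranted, dependent paired samples t-test were run". Alpha is 0.05. The models cover nerve conduction velocity (the primary outcome, Section 5.1) and the three secondary outcomes of Section 5.2.

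Neither Section 6 nor any other section gives a rule for missing values, a deletion rule, an analysis set or a dropout allowance. The SPSS procedure is not named.

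Three other places bear on how data might be lost:

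- Sections 2 and 5.1 give two testing visits, four weeks apart.
- Section 2 has the training arms exercise for four weeks "using a specialized hand-grip kit provided to them", while "Those assigned to the control group were asked to maintain normal daily activities throughout the duration of the four weeks".
- Section 3 plans "recruitment of 80 participants pseudo-randomly assigned to 1 of 4 groups", with no stated allocation ratio.

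**The concern.** Two times by two limbs makes 2 x 2 = 4 values per participant per outcome. A mixed factorial ANOVA in its standard form needs all four, so one failed recording on one hand at one visit removes the other three values as well. Three things would then be at stake.

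- **Precision.** Usable data are discarded and the group x time interval widens.
- **Bias.** Only the training arms carry an exercise task, so loss by visit 2 could differ between training and control. If leaving also depends on the baseline value, a comparison of completers is biased.
- **Consistency.** A paired t-test needs only its own pair. A participant dropped from the ANOVA for one limb could re-enter a t-test on the other, so the two steps could rest on different people.

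**Working it through.** **Inputs.** From the documents: 80 participants, four groups, two visits, two limbs, alpha 0.05. Assumed, because the documents do not give them: 20 per arm; a two-sided test; all rates of missing data; and four covariance structures, whose limb-averaged pre-post correlations r are 0.44, 0.56, 0.75 and 0.85.

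**The plan's own figures.** There is no missing-data figure to reproduce. The sample size above 16 in Section 3 fits a paired two-sided t-test at d = 0.80 (n = 15 at 80% power, 17 at 85%), but neither the test nor the power is stated, and it does not bear on this point.

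**Step 1: complete data.** The mixed model has 16 cell means (2 x 2 x 2 x 2) and an unstructured 4 x 4 covariance. On a complete simulated data set it gives the same group x time estimate (-0.2276), variance (0.01674) and df (80 - 4 = 76) as the ANOVA. Nothing is gained.

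**Step 2: a fraction f of participants lose one recording.** The group x time effect is built from the contrast c = (-1/2, -1/2, 1/2, 1/2) on (pre-left, pre-right, post-left, post-right). Completers-only variance is proportional to c'Vc/(1 - f). With all available values it is c'I⁻¹c, where I averages the inverse covariance of whatever each participant has. The ratio of mixed-model to completers-only variance is below, first with the covariance known and then estimated (10,000 simulated trials per scenario). Power is for an effect of 0.635 SD of change, which has 80% power at 40 v 40.

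| f | Ratio, known | Ratio, estimated | Interval width ratio | Completers-only power |
|---|---|---|---|---|
| 5% | 0.958-0.965 | 0.957-0.962 | 0.977-0.981 | 78% |
| 10% | 0.915-0.929 | 0.909-0.932 | 0.953-0.961 | 76% |
| 15% | 0.871-0.892 | 0.861-0.894 | 0.928-0.939 | 73% |

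Mixed-model power is about 78% to 80% throughout. For scale, if each of the four values were missing independently at 2%, then 1 - 0.98⁴ = 7.8% of participants would be incomplete.

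**Step 3: a fraction f miss visit 2.** With equal pre and post variances and known covariance the ratio reduces to 1 - f(1 - r)/2.

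- f = 10%: 1 - 0.10 x 0.56/2 = 0.972 at r = 0.44, and 1 - 0.10 x 0.15/2 = 0.9925 at r = 0.85.
- f = 15%: 1 - 0.15 x 0.56/2 = 0.958, and 1 - 0.15 x 0.15/2 = 0.989.

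Simulation with the covariance estimated gives 0.974-0.992 and 0.965-0.995. The gain in variance is about 0% to 4%.

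**Step 4: bias.** Suppose 15% leave the training arms only, with the odds of leaving doubling per SD lower baseline. Those who stay then have a mean baseline m = 0.098 SD too high. Change regresses on baseline with slope r - 1, so the bias in SD of change is (r - 1)m/√(2(1 - r)).

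- r = 0.5: -0.5 x 0.098/1 = -0.049.
- r = 0.8: -0.2 x 0.098/0.632 = -0.031.

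The standard error is √(1/40 + 1/34) = 0.233, so these are 0.21 and 0.13 of a standard error. Over the four structures, simulation gives -0.024 to -0.048 (0.10 to 0.20 of a standard error), and the completers-only 95% interval misses 5.3% to 5.6% of the time. Mixed-model bias is 0.003 SD or less.

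If 15% leave **both** groups with the same dependence on baseline, the two biases cancel. With opposite dependence they add: 2 x -0.049 = -0.10 and 2 x -0.031 = -0.06. Equal rates alone are therefore not enough.

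**Step 5: participants in each step.** With one recording lost by a fraction f, the ANOVA uses 80(1 - f) = 76, 72 or 68 participants at 5%, 10% or 15%. A t-test on one limb using every available pair draws on average on 80(1 - f/2) = 78, 76 or 74. The gap is 2, 4 or 6.

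**The case against.** The strongest reply is that little is shown to be at stake. The documents report no missing values. The features that make loss plausible, a second visit after four weeks and an exercise task in one condition, point to a missed visit 2, where Step 3 finds almost no gain. The larger figures in Step 2 need the loss of a single limb recording, and no section describes how that would arise. The bias in Step 4 barely moves interval coverage. Section 6 is also in the past tense, so replacing the model now would be post hoc. All of this stands, and it limits the point to a conditional and modest one.

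The mismatch in Step 5 is likewise conditional. Section 6 does not say whether the t-tests are per limb, averaged over limbs or restricted to ANOVA completers.

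A reader might also count the symptom screen as a cause of missed second visits. Section 2 lists it among the exclusion criteria: anyone who "had identified as symptomatic on the COVID-19 screening questionnaire were not permitted to participate". Whether it was repeated at visit 2 is not stated, so no weight is placed on it. Nor can the slack between 20 per arm and 17 (20 - 17 = 3, or 15%) be read as a dropout allowance; Section 3 does not call it one.

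What does not stand is that the choice of model is mere preference. The mixed model returns the ANOVA's group x time result on complete data and keeps partial records otherwise. Without a rule or counts, a reader cannot tell which case applies.

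**Conclusion.** The omission is real and should be mended, but it is not a fatal flaw. Listwise deletion is inferred from the method named. Given that, and assuming 20 per arm and the covariance structures used:

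- single lost recordings in 5% to 15% of participants cost about 4% to 14% in group x time variance, an interval about 2% to 7% wider than necessary;
- a missed visit 2 costs about 0% to 4% in variance;
- 15% baseline-dependent loss from the training arms alone gives a bias of about 0.02 to 0.05 SD of change.

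A reader might infer that the trial lost data, that its result is biased, or that power fell to 73%. The documents support none of these: they give no counts, and that power figure needs an assumed 15% with one lost recording. A reader might also infer that equal dropout in the two groups removes the bias. It does so only if dependence on baseline is the same too. Confidence is medium, because every rate here is an assumption.

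**What to change.** 1. Report, per arm and outcome, how many participants have all four values. This settles whether the point has any practical effect.
2. Fit a linear mixed model (SPSS MIXED, REML, Satterthwaite df) with the same age x group x time x limb factors and an unstructured 4 x 4 covariance, using all available values from all participants as assigned.
3. Take the pre-post comparisons as contrasts from that model in place of the paired t-tests, so both steps use the same participants.
4. Keep the completers ANOVA as a sensitivity analysis.

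If the analysis is already done, as the past tense suggests, do step 1 first. Only where values are missing, add the mixed model beside the planned ANOVA and label it post hoc.

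The cost is slightly more modelling work in the same package and 10 covariance parameters (4 x 5/2). At n = 80 these did not disturb the error rate in simulation (mixed-model type I error 4.7% to 5.4%). There is no gain with complete data, and no protection if loss depends on unobserved values (missing not at random).

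### Section 6 compares raw pre-to-post changes; adjusting visit 2 for the visit-1 value already collected, with a separate slope in each age group, is an optional and cheap gain in precision

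*Combined protocol and SAP*

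**What the plan says.** Section 6 specifies a four-way mixed factorial ANOVA with factors age, group, limb and "time [pre vs. post"; the models "were conducted to determine changes in NCV, nCSA, max strength, and dexterity". Visit 1 enters only as the first level of time, and no covariate is named. The section is in the past tense: "All statistical analyses were performed using SPSS Version 26".

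Section 2 says that at both visits "nerve conduction velocity, nerve cross-sectional area, maximal hand grip strength, and hand motor dexterity were measured", so a baseline value was planned for all four outcomes. Within each age range, participants were "pseudo-randomly assigned to either the intervention group or control group"; the method is not described.

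Section 4 includes the aim "to determine if age affects nerve plasticity in response to training". Section 3 says "Power calculations indicated that a sample size of > 16 was sufficient power", at a Cohen's d of magnitude 0.80 and alpha 0.05, with 80 to be recruited into four groups. It states no numeric power, no test and no SD for the d. No section gives a visit-1 to visit-2 correlation or an SD at either visit.

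**The concern.** A change score fixes the coefficient of the baseline value at 1. When assignment is random, estimating that coefficient from the data usually gives a smaller variance for the same training contrast. The covariate is already in the dataset, so the precision costs almost nothing.

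It matters most for the section 4 question about age. That question is a difference between two training-minus-control differences, so with equal arms and equal variances its variance is twice that of the contrast within one age group. It is the least precise of the training contrasts, and a modest saving in variance is worth most there.

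**Working it through.** **Inputs.** From the documents: 80 participants, four groups, two visits, alpha 0.05, d of magnitude 0.80. Assumed: 20 per arm, all complete, two-sided tests, and every value of the pre/post correlation (rho) and of k, the visit-2 SD divided by the visit-1 SD. Both refer to participant means over limbs.

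**1. The plan's own figure.** The sample size above 16 cannot be reproduced uniquely, because test and power are missing. At d = 0.80, a two-sided paired t-test needs 15 for 80% power and 17 for 85%. A two-sample t-test needs 26 per group for 80%, and 17 per group gives 62%. The figure fits a within-group paired calculation, but the plan does not say so.

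**2. What group by time tests.** On a generated four-arm dataset, the group by time F and the squared t on limb-averaged change scores were both 1.5626. The residual df is 80 − 4 = 76.

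**3. Variance ratio, adjusted to change score.**

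Ratio = [k²(1 − rho²) / (1 + k² − 2k·rho)] × (1 + c)

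The first factor is at most 1, reached when the true slope k·rho equals 1. The term c is the expected cost of estimating the slope:

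- one slope for all arms: c = 1/(76 − 2) = 1/74 = 1.4%
- a separate slope per age group (40 people, two arms, 38 df): c = 1/(38 − 2) = 1/36 = 2.8%

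With k = 1 the first factor reduces to (1 + rho)/2:

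| rho | (1 + rho)/2 | one slope, × 75/74 | separate slopes, × 37/36 |
|---|---|---|---|
| 0.5 | 0.75 | 0.76 | 0.77 |
| 0.7 | 0.85 | 0.86 | 0.87 |
| 0.9 | 0.95 | 0.96 | 0.98 |

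The one-slope column also requires equal slopes in the two ages. If the SD rises between visits, the gain can vanish. At k = 1.2 and rho = 0.8 the first factor is 1.44 × 0.36 / (2.44 − 1.92) = 0.5184/0.52 = 0.997, so separate slopes give 0.997 × 37/36 = 1.02.

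**4. One slope when the ages differ.** Take k = 1 and a visit-1 SD of 1 in the young. The pooled slope b is the average of the two ages' slopes, weighted by baseline variance. Before estimation cost, the young ratio is (1 + b² − 2b·rho) / (2 − 2rho), using the young rho.

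| Young rho / older rho | b | Young ratio, large sample | Simulated |
|---|---|---|---|
| 0.9 / 0.6 | 0.75 | 0.2125/0.2 = 1.06 | 1.10 |
| 0.9 / 0.5 | 0.70 | 0.23/0.2 = 1.15 | 1.17 |
| 0.9 / 0.5, older SDs 1.5 times larger | (0.9 + 2.25 × 0.5)/3.25 = 0.623 | 0.267/0.2 = 1.33 | 1.40 |

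The simulations used four arms of 20, and repeat runs differ by up to 0.06. The excess over the large-sample figure is mainly the cost of estimating the slope. In the same settings, separate slopes gave 0.97 to 0.98 for the young contrast, in line with 0.95 × 37/36 = 0.98.

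**5. Illustrative power only.** Suppose d = 0.80 is a training-minus-control difference in change-SD units, and for the age question an effect in the young only. The noncentrality is 0.8·√10 = 2.53 within age and 0.8·√5 = 1.79 for age by group. On 76 df, change-score power is 70% and 42%. Dividing by the square root of the separate-slope ratio and using 74 df gives 81/76/71% within age and 52/47/43% for age by group, at rho 0.5/0.7/0.9. In the worst case (ratio 37/36) power is 69% and 41%. If d is in outcome-SD units instead, at rho 0.7 and k = 1, d becomes 0.8/√0.6 = 1.03 and change-score power is 90% and 63%.

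**The case against.** **The planned test is valid and matches the stated interest in change.** This stands. Nothing in the documents supports a reading that the ANOVA is biased or wrong. The gain from adjustment is unknown and may be nil.

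**A reader might infer that adjustment can never cost more than about 1.4% of variance.** The documents do not support that. It is the price of one slope common to all arms, and it holds only if young and older adults share that slope. Nothing in the plan gives grounds to assume so for ages 18-35 and 60+, and section 4 asks whether the ages differ in plasticity. If the slopes differ, a common slope can inflate the variance by roughly 10 to 40% in one age group (step 4), although the other age group and the age by group contrast still gained in the simulated settings. Separate slopes remove this problem for a worst expected loss of 2.8%.

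**A reader might also take 70% and 42% as the plan's own power.** They are not. Section 3 states no power and no test, and its figure fits a paired calculation at least as well. Low power for the age question is mainly a matter of sample size, which adjustment does not cure.

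**It may be too late, and assignment may not have been random.** Both stand as conditions. The past tense suggests that the analysis may already have been run, in which case the primary inference gains nothing. If the pseudo-random assignment was not effectively random within age, the two analyses can answer different questions and the precision claim lapses.

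**Conclusion.** The point holds as an optional, cheap improvement. Section 6 tests raw changes and makes no use of the visit-1 value as a covariate. Under effectively random assignment within age, adjustment with a separate slope per age group has an expected variance between about 0.77 and 0.98 of the change-score variance for rho from 0.5 to 0.9 with equal SDs, and at worst about 1.03 of it.

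This rests on assumed correlations and SDs and on 80 completers split equally. With 68 completers (34 per age group) the worst loss becomes 1/(32 − 2) = 3.3%. These losses are averages over chance baseline imbalance, so a single trial with marked imbalance could lose more. That the tests are change-score tests is certain; the size of any gain is not.

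**What to change.** Add to section 6, in substance:

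> For each outcome, visit-2 values are analysed in a linear mixed model with age, group, limb and all their interactions as fixed effects and a random intercept for participant. The covariate is the participant's visit-1 mean over limbs, centred within age group, with a separate slope for each age group. Training minus control is reported with a 95% CI in each age group, together with the difference between the two.

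Age was not assigned, so the adjusted young-versus-older main effect should not be read causally.

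**Role.** Make this model primary for the training contrasts only if the data have not been analysed. If they have, keep the ANOVA primary and label this model supportive and post hoc. Report both either way; if they disagree, the conclusion follows the one named primary and the disagreement is stated.

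**Assignment.** State how the pseudo-random assignment was carried out. If it was not effectively random within age, show both analyses without calling the adjusted one more precise.

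**Cost.** No new data, and the SPSS mixed-model procedure suffices. The price is a paragraph of text, two between-person residual df (74 instead of 76), a worst expected variance loss of about 2.8%, and a second model for each of four outcomes.

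### The only follow-up named after the ANOVA is a paired t-test with no stated trigger, and it cannot show that training beat control in young or in older adults

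*Combined protocol and SAP*

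**What the plan says.** Section 6 (Analyses) crosses age, group, time and limb in a mixed factorial ANOVA. These models "were conducted to determine changes in NCV, nCSA, max strength, and dexterity". The follow-up is one sentence: "If warranted, dependent paired samples t-test were run". It does not say which model term or p-value triggers the tests, which pairs are compared, or for which outcomes. The section closes with "An alpha level of 0.05 was used for all comparisons". It names no comparison between arms other than the ANOVA terms.

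The aim in Section 4 is "To quantify the effects of resistance training on nerve conduction velocity in young and older adults and to determine if age affects nerve plasticity". Section 2 gives each age group its own control arm: "Those assigned to the control group were asked to maintain normal daily activities throughout the duration of the four weeks". Section 3 plans "recruitment of 80 participants pseudo-randomly assigned to 1 of 4 groups".

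**The concern.** Age and group are between-person factors. A paired test can compare before with after, or left with right, but it cannot compare Arm 1 with Arm 2 or Arm 3 with Arm 4. The omnibus terms do not fill the gap. Group × time compares training with control averaged over age, and age × group × time tests whether that difference varies with age. Neither gives a training-minus-control estimate or interval within young or within older adults.

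The control arms are there so that any four-week change without training can be subtracted. A paired test in a trained arm leaves that change in. If all arms drift alike, for example through familiarity with the tests, a trained arm can reach significance while its control arm just misses, and the result may be read as a training effect. Whether this is common or rare depends on the unwritten trigger.

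**Working it through.** **The plan's own figure.** Section 3 says more than 16 is enough at an absolute d of 0.80 and alpha 0.05, without stating the test, sidedness or power. It therefore cannot be reproduced uniquely. By exact noncentral t, two-sided:

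- A paired test needs 15 for 80% power and 17 for 85%. Its power is 0.85 at 16 and 0.87 at 17.
- A two-sample test on change needs 26 per arm for 80%. Its power is 0.69 at 20 per arm.

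The stated number is compatible with a within-arm test. This is suggestive only.

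**Inputs.**

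- From the documents: 80 participants in four groups (Section 3); alpha 0.05 (Section 6).
- Assumed: an equal split, 80/4 = 20 per arm; two-sided tests; change averaged over limbs, with SD 1 in every arm; retest shift s of 0–0.8 SD, the same in all arms; training effect d of 0, 0.5 or 0.8 SD. The documents give no SD and no shift.

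**Tests.** Paired: t = mean change / (SD/√20), 19 df. ANOVA terms and between-arm contrasts use the pooled error, 76 df. The between-arm contrast in one age has standard error SD × √(2/20). Holm tests the smaller of the two p-values at 0.025 and the larger at 0.05. Each scenario was simulated 200,000 times. The false pattern is a significant paired test in the trained arm and a non-significant one in the control arm of the same age.

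**Exact check.** At s = 0.5 a paired test rejects with probability p = 0.565. The false pattern in one age has probability p(1 − p) = 0.565 × 0.435 = 0.246. In at least one of two ages it is 1 − (1 − 0.246)² = 0.431. The time effect is significant with probability 0.993, so requiring it removes almost nothing.

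**Scenario 1: no training effect, shared shift s.** False pattern in at least one age, by trigger. The last column is any false training claim from ungated Holm-adjusted contrasts.

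| s | time effect | group × time | either interaction | Holm contrasts |
|---|---|---|---|---|
| 0.2 | 15.2% | 2.0% | 4.5% | 4.9% |
| 0.3 | 30.4% | 2.4% | 5.6% | 5.0% |
| 0.5 | 43.1% | 2.5% | 6.2% | 4.9% |
| 0.8 | 13.6% | 1.5% | 3.0% | 4.9% |

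**Scenario 2: training works in one age only, same shift in all arms.** False pattern in the non-responding age, as a share of all trials, with paired tests run separately by age and arm. The last column is a false claim in that age from the Holm contrasts.

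| d | s | group × time | either interaction | three-way only | Holm contrast |
|---|---|---|---|---|---|
| 0.5 | 0 | 1.6% | 3.1% | 1.6% | 3.1% |
| 0.5 | 0.2 | 5.9% | 6.1% | 0.5% | 3.1% |
| 0.5 | 0.3 | 8.8% | 9.0% | 0.6% | 3.2% |
| 0.5 | 0.5 | 10.9% | 11.0% | 0.7% | 3.1% |
| 0.8 | 0 | 2.3% | 4.2% | 2.3% | 4.1% |
| 0.8 | 0.2 | 9.3% | 9.5% | 1.6% | 4.1% |
| 0.8 | 0.3 | 14.2% | 14.3% | 2.4% | 4.0% |
| 0.8 | 0.5 | 18.3% | 18.4% | 3.2% | 4.0% |

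The responding age opens the group × time trigger, and the paired test then credits the other age with the shared shift.

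**Sensitivity.** With 17 per arm and s of 0.3–0.5, scenario 1 gives 27–44% (time effect), 2.3–2.4% (group × time) and 5.3–6.1% (either). Scenario 2 with the group × time trigger gives 7–17%.

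**Limit of the between-arm contrasts.** With equal true effects in both ages and no change in controls, the Holm contrasts are significant in exactly one age in 31% of trials at 0.5 SD and 35% at 0.8 SD. The three-way term rejects in 5%.

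**The case against.** The strongest reply is that the plan already tests training against control. Group × time and age × group × time are in the model and correspond to the two parts of the Section 4 aim. On this view, what is missing is a simple-effect contrast, and young and older adults could be read as the study population, not as two separate questions. The larger figures also need unfavourable readings:

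- **Time-effect trigger.** Time has two levels, so a significant time effect needs no t-test to interpret it. About 26 of the 30 percentage points at a 0.3 shift, and 37 of the 43 at 0.5, come from trials in which neither interaction is significant. A false claim there means disregarding the plan's own interaction tests.
- **Group × time trigger.** The 9–18% assumes follow-up split by age after a term that does not involve age. If splitting requires the three-way term, the rate is 0.6–3.2%, no worse than the Holm contrasts.
- **Retest shift.** None is documented, for nerve conduction velocity or any other outcome. Nor does Section 6 say that a significant trained arm beside a non-significant control arm would be reported as a training effect.

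All of this stands as a limit on the size of the harm, and 30–43% should not be taken as the expected error rate. It does not rescue the follow-up. The plan neither states nor excludes any of these triggers. Under every one of them, and with no shift at all, a paired test still does not estimate training minus control in either age.

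**Conclusion.** The concern holds and should be fixed. It is confined to the follow-up; the ANOVA is valid. Two facts rest on the text alone: the trigger is undefined, and no between-arm comparison within an age group is named. The harm is conditional on 20 per arm, unit SD of limb-averaged change and a shared shift that the documents do not give. At a shift of 0.3–0.5 SD it is large if a time effect suffices, and small if an interaction is required and training does nothing. It is moderate if group × time (or either interaction) is required, training works in one age only, and the paired tests are split by age. With no shift, the paired tests produce no more of these false patterns than between-arm contrasts do.

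**What to change.** 1. Replace the paired t-tests as the inferential follow-up with the training-minus-control difference in change within each age group. Report both differences with 95% CIs whether or not an interaction is significant, and Holm-adjust the p-values over the two ages. No trigger is then needed.
2. State that a claim that age alters the response rests only on the age × group × time estimate with its 95% CI, never on which age-specific result is significant. This binds the new contrasts too, given their 31–35% split rate under equal effects.
3. Keep before-to-after changes within arms as description only.
4. Section 6 is in the past tense. If the analyses are already done, label these contrasts post hoc.

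The cost is SAP wording and two contrasts in the same software, with no new data. Intervals widen: the 95% half-width is 2.093/√20 = 0.47 SD within an arm, 1.992 × √(2/20) = 0.63 SD for training minus control in one age, and 1.992 × √(4/20) = 0.89 SD for the age difference in that contrast. Power is modest: a Holm-adjusted contrast detects an effect present in one age only in about 25% of trials at 0.5 SD and 60% at 0.8 SD.
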